Hypothesis 1: Assuming a correlation of pre- and post-test conservatively: reliability of 300 followers will be required. If the correlation between pre- and post is larger, smaller sample sizes are required. Thus, a sample of 300 Blacks and 300 Hispanics is adequate to examine the within-subject change using a paired t-test. The pre-post-test for binary outcomes (% of isolates) is McNemar's test. The minimum required sample size is 208. Thus, the proposed sample sizes will be adequate to test within-group differences.

Hypothesis 2: The total minimum required sample size in each ethnic group (Black and Hispanic) will be 192 for a total of 385 with effect size 0.332 (Cohen's d). Assuming that α =0.05, 1- β =0.80 (power), the total minimum required sample size for the two groups (Black and Hispanic) with effect size 0.1525 (P_0 - P_1) is **318** (**159 per group**).

Data analysis: Extensive processing is required before the actual data analysis, which comprises data science methods and statistical tests for our hypotheses.

Data processing: We will process Twitter data for data analyses through several steps:1) merging of data files in our institutional high performance computing (HPC) environment (Habanero), 2) converting XML to txt file format into a human-readable format for integrity checking, 3) feature selection, and 4) indexing.³⁵

Data science analyses for publicly available de-identified data: We will use a variety of software packages (R, Python, Nvivo, ORA, NodeXL, SAS) for the data science analyses. Since Twitter user demographics and personal data are not directly available, we will apply algorithms to users' Tweets and images to estimate their demographics, including those considered Social Determinants of Health.³⁶⁻³⁹ We will stratify those variables into categories for data analysis procedures as relevant. To answer research question 1, we will descriptively characterize (e.g., #Tweets, # followers, #likes, #retweets) Twitter activity in the two networks. To address the second research question, we will apply Syuzhet sentiment analysis and LDA to characterize negative affect scores and topic models, respectively. For the third research question, we will compute the network measures listed in **Table 1**.

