Emotional valence, expressing topics, and conversational styles in macro-,meso- and micro-level among de-identified Twitter followers will be computed from publicly available Tweet data. Unlike the traditional methods, data science methods such as natural language processing (NLP) and network analyses enable us to detect emotional valence score, changes in topics, volume of isolates, and communication styles without asking the users any questionnaires. The following table summarizes concepts, measurements, units of analysis, and data science analytic methods.

Table 1. Concepts, Measures, Data Science Methods and Units of Analysis

	Concept	Measures [§]	Data Science Methods	Unit
Content	Emotional valence ⁴⁰	Emotional valence score ^{18, 40-45} detected from text data (e.g., "This is so helpful" – emotion score +4, "I am sad"- emotion score -6)	Syuzhet packages 46	***
	Social support (informational, instrumental, emotional, appraisal)	Topic changes in social support ^{17, 19-21}	Topic modeling using hierarchical ⁵¹ and n-gram embedded LDA algorithms ⁵¹⁻⁵⁴	***
ø)	Social network: Macro- level ⁵⁵	The volume of isolates, Network type, Density, Centralization, Cohesiveness 26, 27, 55, 56	Network analysis ¹⁷⁻ 20, 23, 24, 26, 27	***
Structure	Social network: Meso- level ^{57, 58}	Size and number of communities, the volume of the community activities, leaders of community ^{26, 27, 56, 57}	Clauset-Newman- Moore ⁵⁹ Girvan-Newman ⁵⁸	**
	Social network: Micro- level ⁶⁰	16 communication types among triad, number of individual posting activities 26, 27, 56, 57, 60	Triad census analysis ⁶⁰	*

^{*} individual level, ** community level, *** global network level, §all measures in real-time)

Statistical Analyses: Pre-post comparisons will be examined from baseline (3 months pre-intervention) to 3 months (9-12) months after initiation of the intervention. Analyses of pre-post mean differences will be performed using SAS PROC TTEST, PROC Mixed, PROC GLIMMIX, and PROC CATMOD, with adjustments for the correlation within participants induced by repeated measures and for unreliability and missing data treatment. The continuous outcome will be analyzed using SAS PROC TTEST, PROC Mixed, and the binary outcome will

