be analyzed using PROC GLIMMIX or PROC CATMOD (for the McNemar test), depending on the missing data. We will compare measures among the two groups using independent t-tests for continuous variables and Chisquare tests for proportions to test the second hypothesis. Machine learning-based trend analysis 61, 62 will be applied for the continuously detected emotional valence score.

[figure not shown]
3. Study Procedures

Procedure: Publicly available Tweet data (e.g., Tweets, time stamp, self-reported location) from de-identified Twitter followers of our Twitter sites will be obtained from the public database. No personally identifiable information (PII) under the definition used by the National Institute of Standards and Technology (NIST) such as names, addresses, date of birth, and email addresses will be collected. We will analyze publicly available Tweet data for emotional valence (auto-estimation from Tweet messages), topic changes, the volume of isolates, size and number of communities, and communication types for our outcome variables. In addition, three demographic elements (i.e., self-reported age, gender, race/ethnicity, which are un-linkable to their PIIs) will be collected to examine general confounders. Again, no PII will be used or accessed.

Intervention: Two Tweeters, including a bilingual Hispanic, will strictly follow the intervention delivery protocol developed in Aim 2 with guidance from the Tweet-S2 Expert Panel. Daily for 365 days that cross Years 3 and 4, the Tweeters will post a Tweet from the Tweet library to each Twitter community alternating among those related to information, instrumental, emotional, and appraisal support. The Tweeter will also engage in social network activities by replying to, liking, and retweeting messages posted by others. This intervention will be consistently conducted (e.g., time, center brand themes, designs) to enhance intervention fidelity.⁶³ After a Tweet is posted, followers can respond using Twitter functions (e.g., retweet to quote and disseminate our Tweet message, posting a Tweet message to express their after thoughts and questions using @mention, like. and reply function). In addition, the P.I. will examine the archive files to monitor intervention fidelity and reinforce expected behaviors of the Tweeters as needed.

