Publicly available Twitter data collection: During the baseline (3 months pre-intervention) and intervention (365 days crossing Years 3 and 4) periods, we will collect publicly available Tweet messages and associated metadata (e.g., userID, relationship, time stamp, Tweet, Hashtags, Twitter page, geo code, location, type) daily. We will also double-check the data integrity (e.g., incompletely captured data) daily. In terms of missing Twitter data,⁶⁴ we will make an effort to minimize missing data in 3 ways: our designated Tweeters and the P.I. will be available during data collection, two collection tools (NodeXL and NCapture) will be used, and collection of Tweets will be monitored daily to ensure that capture was adequate and with no PII. Figure 1 shows an example of publicly available data collected.

Figure 1. An example of publicly available data collected via NodeXL: Vertex 1 and 2 will be used for macro, meso, and micro level network analyses. Tweet text with no personal identifiers will be used for text analyses, including emotion score calculation and topic modeling.

upon following Twitter networks

will be strictly prohibited and daily monitored/removed.

4. Study Drugs or Devices

Not applicable

5. Study Instruments (e.g., Questionnaires, Interview Outlines, Focus Group Guides) **No direct instrumentations** such as questionnaires (i.e., survey, interview) will be applied for the outcome measurers. Instead, emotional valence, topics, and conversational styles in macro-,meso- and micro-level among **anonymous Twitter followers** will be computed from the publicly available Tweet data. Unlike the traditional methods, data science methods such as natural language processing (NLP) and network analyses enable us to detect emotional valence score, changes in topics, volume of isolates, and communication styles without asking the users. Table 1 above in Data Analyses summarizes concepts, measurements, units of analysis, and data science analytic methods.

6. Study Subjects

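### The Hypothesis 1 pre-post tests have no trend term and no untreated network, so a difference between windows centred 12 months apart cannot be told apart from drift already under way

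*Combined protocol and SAP*

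**What the plan says.** Hypothesis 1 concerns differences within each network. Section 2 (Statistical Analyses) fixes the two windows: "Pre-post comparisons will be examined from baseline (3 months pre-intervention) to 3 months (9-12) months after initiation of the intervention".

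- **Tests.** For the continuous outcome, Section 2 (Hypothesis 1) says that 300 followers per network "is adequate to examine the within-subject change using a paired t-test". For the binary outcome, "The pre-post-test for binary outcomes (% of isolates) is McNemar's test".
- **Models.** The plan lists SAS procedures for the pre-post mean differences, and the adjustments that it names for them read "with adjustments for the correlation within participants induced by repeated measures and for unreliability and missing data treatment". No term for time is named.
- **Trend.** The one analysis of the series over time is this: "Machine learning-based trend analysis 61, 62 will be applied for the continuously detected emotional valence score". It is not tied to a hypothesis, has no stated term for the start date and no stated test, and does not mention isolates.
- **Data.** Section 3 (Publicly available Twitter data collection) provides for daily capture: "During the baseline (3 months pre-intervention) and intervention (365 days crossing Years 3 and 4) periods".
- **Design.** Section 2 (Design) describes a non-equivalent two-group pre-post study in which the two groups are the Black and the Hispanic network. Both receive the Tweets, so there is no untreated series.

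**The concern.** A contrast of two windows measures everything that changed between them. With no trend term and no untreated network, that includes any change in valence or in unanswered Tweets that was already under way before the first study Tweet. Windows centred a year apart cover the same part of the calendar, which deals with season but not with a slow rise or fall across years.

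What is at stake is attribution. The paired t-test and McNemar's test can answer whether the later window differs from the earlier one. They cannot say whether the intervention made the difference. Daily data could show whether the level or slope changes at the start date, but the plan specifies no analysis that asks this.

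**Working it through.** **1. The plan's own figure.** Section 2 gives 300 followers for the paired test but no effect size, SD or correlation, so 300 can be neither reproduced nor refuted. Solved backwards, 300 pairs detect a standardised paired difference of 0.162 with 80% power (two-sided 0.05).

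**2. The windows.** Baseline is months −3 to 0, centre −1.5. Follow-up is months 9 to 12, centre 10.5. Centre to centre: 10.5 − (−1.5) = 12 months. Edge to edge: 9 months. With a 91-day follow-up window, 365 − 91 = 274 intervention days (75%) lie outside the Hypothesis 1 contrast.

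**3. What drift does to the paired t-test.** Inputs:
- From the documents: 300 pairs (Section 2), and 160 pairs, which is 400 × (1 − 0.60) from the attrition in Section 7.
- Assumed, because the documents give neither: linear drift of 0.005, 0.01 or 0.02 SD per month, and pre-post correlation r from 0.3 to 0.7. The intervention effect is set to zero.

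The expected difference is 12 × drift, its standard error is √(2(1 − r)/n), and their ratio is the non-centrality of the t-test. Example: drift 0.01, r = 0.5, n = 160 gives 0.12 / √(1/160) = 0.12 / 0.0791 = 1.52, and the test rejects 33% of the time.

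| Drift (SD/month) | Shift over 12 months (SD) | Rejects, 160 pairs | Rejects, 300 pairs |
|---|---|---|---|
| 0.005 | 0.06 | 10–16% | 14–27% |
| 0.01 | 0.12 | 25–50% | 42–76% |
| 0.02 | 0.24 | 72–97% | 94–100% |

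Ranges run from r = 0.3 to r = 0.7 and use the noncentral t distribution. A normal approximation gives 73–98% for 160 pairs at drift 0.02. A larger sample raises the rate. At drift 0.01 and r = 0.7 the standardised paired difference is 0.12 / √0.6 = 0.155, close to the 0.162 that 300 pairs detect with 80% power. The same reasoning applies to McNemar's test, but no figure is given because the plan states no discordant proportions.

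**4. What a segmented model can and cannot do.** Take 13 baseline and 52 intervention weeks and fit

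Y(w) = b0 + b1·w + b2·post + b3·post·w + error,

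where b2 is the level change at launch and b2 + 45.5·b3 is the effect at the centre of months 9–12. Assume a weekly SD of 0.1 and lag-one autocorrelation of 0 or 0.2.

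| Quantity | SE, autocorrelation 0 | SE, autocorrelation 0.2 |
|---|---|---|
| Level change at launch | 0.062 | 0.071 |
| Effect at month 10.5 | 0.387 | 0.446 |
| Two-window difference | 0.039 | 0.047 |

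Under independent errors the month-10.5 SE is 0.387 / 0.039 = 9.9 times that of the two-window difference. A daily version (90 + 365 days) gives 1.49 against 0.15, about 10 times.

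In simulated series of this kind (2,000 per setting, no effect), the segmented model rejected 3–7% or 7–10% of the time at every drift, depending on how autocorrelation was corrected. The two-window test rejected 79–100% under drift. Power is the other side. For an effect that builds up to 0.12 or 0.30 by month 10.5, the slope-change term has about 6% or 12–14% power with known autocorrelation. In simulation, the level term detected an immediate step of 0.30 in 99–100% of series.

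**The case against.** **The test does what it is labelled to do.** Hypothesis 1 is a within-group difference. If valence really moved by 0.12 SD, a difference exists and rejecting is correct. This stands. The fault is in attribution and comes from having no untreated network. A reader might infer that the paired test's standard error is wrong, but linear drift shifts what the difference means and is not a standard-error defect.

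**The segmented model should not replace the paired test.** This also stands. A year of daily posts and monthly chats could well work gradually, and on the figures above the model would mostly miss such an effect. In addition, the paired test follows the same people, whereas weekly network means let membership in. Advertising runs in Years 3 and 4, outreach is monthly and 60% attrition is expected, so turnover could itself create a level or slope change.

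**Months 0–9 may be used elsewhere.** A reader might infer that these months enter no test at all. The documents do not support that. The 9–12 month window is stated only for the pre-post comparisons. For Hypothesis 2 the plan says "We will compare measures among the two groups using independent t-tests for continuous variables" and gives no window. The valence trend may also use the whole series.

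**The drift is assumed.** True. A reader might take the rejection rates as evidence that drift is present, but nothing in the documents shows drift or its size.

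**PROC MIXED could carry a time term.** It could, but the plan names none, and the adjustments it lists concern correlation, unreliability and missing data.

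**Conclusion.** The point holds for the Hypothesis 1 pre-post tests. They compare windows centred 12 months apart without a trend term or an untreated series, and the valence trend analysis, as written, does not fill the gap. A significant result would show that the later window differs from the baseline, and no more.

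How much this matters depends on drift that the documents do not give. Within the assumed range, false attribution runs from about 10% (0.005 SD per month, 160 pairs, r = 0.3) to nearly 100% (0.02, 300 pairs, r = 0.7), against a nominal 5%. These figures assume linear drift common to all followers and complete pairs.

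The documents do not support going further and making segmented regression the sole Hypothesis 1 test. Thirteen baseline weeks support an estimate of a change at launch, not of a 12-month effect. The useful step is a supporting analysis that limits what may be claimed.

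**What to change.** 1. Keep the paired t-test and McNemar contrast as the Hypothesis 1 test, and state that it estimates a pre-post difference and not an intervention effect.
2. In place of the machine-learning trend, specify for each network a supporting segmented regression of weekly mean valence and weekly % isolates over 13 baseline and 52 intervention weeks. Include baseline trend, level change and slope change at the start date, autocorrelated errors and a small-sample correction.
3. Name the level change at launch as its main estimate, and report the month-10.5 effect with its interval.
4. Run it on followers present from baseline, with all followers as a sensitivity analysis.
5. State that a pre-post difference will be attributed to the intervention only if this model supports it, and that lack of support is not evidence of no effect.

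**Cost.** Analysis-plan wording only, because the plan already provides for the data. The baseline slope will be very imprecise, so the model has little power for gradual effects. It also cannot exclude an outside event that coincides with launch. The number of followers present from baseline is not known from the documents and may be small.

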Design: The study purpose will be achieved through a quasi-experimental design (non-equivalent 2 group pre and post-test design). The intervention group is **anonymous followers** of two Twitter accounts established: the African American/Black dementia caregiver group and the Hispanic dementia caregiver group. **No personally identifiable information (PII)** under the definition used by the National Institute of Standards and Technology (NIST) such as names, addresses, date of birth, and email addresses will be collected. Instead, we will analyze publicly available Tweet data for network engagement (count of pressing 'like,' 'retweet,' 'reply' button), emotional valence (auto-calculation from Tweet text messages: "this is so helpful"-emotion score +4, "I face many challenges"- emotion score -6), topic changes, the volume of isolates, size and number of communities, and communication types for our outcome variables. To examine general confounders, **three demographic elements (self-reported age, gender, race/ethnicity, un-linkable to name, phone, email, or address)**.

The intervention is summarized in table 1 and comprises the posting of one Tweet per day, replying or directly messaging followers, liking someone else's Tweet, retweeting someone else's Tweet, and a monthly Twitter chat at an established time. The Tweet messages which the IRB will approve from our Aim 2 will be used as an intervention. In addition, Twitter who re-confirm Twitter terms of the agreement, including privacy policy and terms of service (Appendix attached), will be required for this study. If someone decides to follow one of our accounts (i.e., participate in the intervention) and subsequently changes their mind, they can easily change stop following our networks. We will retain our de-identified Twitter followers for our Twitter communities in multiple ways: 1) we will invite caregivers in the dementia caregiver registries (including the NHiRP project), who agreed to be contacted for the future study, developed by Drs. [name] and [name] to follow the relevant Twitter accounts; 2) we will use online advertising function for marketing our Twitter communities using TwitterAds (15 days in Year 3 and 15 days in Year 4); 3) research flyers will be posted in relevant clinics; 4) we will send an invitation via Twitter to the publicly available user IDs (estimated Black user

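### Valence and topic scoring does not separate study-written text from follower-written text, so the Hypothesis 1 pre-post change can partly reflect copies of the intervention's own Tweets

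*Combined protocol and SAP*

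**What the plan says.** Section 3 (Intervention) states that, for 365 days, "the Tweeters will post a Tweet from the Tweet library to each Twitter community", rotating among informational, instrumental, emotional and appraisal support. Followers may respond by several routes, one of which is to "retweet to quote and disseminate our Tweet message". Table 1 (Twitter-based Intervention) adds a monthly hosted chat.

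The data are public Tweets "from de-identified Twitter followers of our Twitter sites will be obtained from the public database" (Section 3, Procedure). Section 2 (Design) describes valence as an "auto-calculation from Tweet text messages". The Figure 1 caption states what enters scoring: "Tweet text with no personal identifiers will be used for text analyses, including emotion score calculation and topic modeling". Table 1 (Concepts, Measures, Data Science Methods and Units of Analysis) gives the social support measure as "Topic changes in social support", over the same four support types.

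Section 2 (Data processing) lists merging, conversion, feature selection and indexing. Section 2 (Statistical Analyses) compares the 3 months before the intervention with months 9-12 after it starts. The metadata collected include "e.g., userID, relationship, time stamp, Tweet, Hashtags, Twitter page, geo code, location, type".

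**The concern.** A retweet of a library Tweet is a post by a follower whose words were written by the study. If it is scored like any other follower post, the study's wording is recorded as the caregiver's emotion and as a support topic. Retweets appear elsewhere in the plan only as an engagement or activity count and as a function open to followers. No rule keeps their text out of the content outcomes.

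The problem runs one way in time. Library text does not exist at baseline and is posted throughout the later window, so the pre-post difference does not cancel it. Hypothesis 1 has no concurrent untreated group that would reveal it. For topics the overlap is close to circular, because the library is organised by the categories being measured. A rise in valence or support topics could be read as change in caregivers when part of it is recirculated script.

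**Working it through.** The plan has no figure to reproduce here: it gives no copied share, no library valence score and no SD. The check has two parts.

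**Is study text kept out anywhere?**
- Source of text: followers' public Tweets, with no split between original and copied words (Section 3, Procedure).
- Filter on scored text: absence of personal identifiers only (Figure 1 caption).
- Processing: four steps, none described as removing retweets, quotes, duplicates or study posts (Section 2, Data processing).
- Metadata: user ID and a type field are collected, but no exclusion rule uses them (Section 3, Publicly available Twitter data collection).
- Timing: at one Tweet a day, each account posts none in the baseline and about 3 × 30 = 90 in months 9-12.

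Followed as written, the plan allows study-written text into the later window only.

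**How large could the effect be?** Let f be the share of a follower's scored later-window text that is copied from the study, and let the follower's own writing stay unchanged.

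Later mean = (1 − f) × own mean + f × library mean, so

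shift = f × (library mean − own mean).

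Divide by the SD of follower-level change and call the standardised gap g. The standardised shift is f × g. This takes f as equal across followers. The sample size is the plan's 300 per group for the paired t-test (Section 2, Hypothesis 1), with two-sided α = 0.05. Both f and g are assumptions.

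| g (SD) | f | f × g | Chance of p<0.05, n = 300 |
|---|---|---|---|
| 0.5 | 10% | 0.05 | 14% |
| 0.5 | 20% | 0.10 | 41% |
| 1 | 10% | 0.10 | 41% |
| 1 | 20% | 0.20 | 93% |
| 2 | 10% | 0.20 | 93% |
| 2 | 20% | 0.40 | over 99% |

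With no copied text the chance is 5%. The paired test has 80% power at a standardised shift of 0.162, which is reached at f = 0.162/g: about 32% for g = 0.5, 16% for g = 1 and 8% for g = 2. If the 60% attrition in Section 7 left 400 × 0.4 = 160 followers, the two g = 1 rows would fall to 24% and 71%.

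**Hypothesis 2.** The between-group bias is the difference between the two communities' shifts. With equal share and equal gap it is zero. If the shares differed by 10 percentage points at a gap of 1 SD, the standardised difference would be 0.10, and the chance of p<0.05 at 192 per group would be 0.165.

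**The case against.** The plan never says outright that retweets are scored. It counts them as engagement, leaves feature selection undefined, and collects fields that could support a filter. It says followers can retweet, not that they are expected to or how often. All of that stands, so the point is about what the written rule allows. An unwritten filter is not a pre-specified one, and the one filter stated for scored text would not remove library Tweets.

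A reader might infer that the shift also threatens Hypothesis 2 on the scale of its planned effect, d = 0.332. The documents do not support this. That figure is a difference between the Black and Hispanic groups, both accounts post one library Tweet a day, and a shift common to both cancels.

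The size is also open. The plan's example scores cannot supply the gap: the +4 belongs to a phrase that reads like a follower's comment, and informational or instrumental Tweets may score near neutral. Followers may have retweeted supportive text from other accounts at baseline, and copies of study Tweets may displace some of that. Upward bias in valence needs library text to be more positive than follower text. Section 1 makes this plausible by reporting mainly negative sentiment among Hispanic caregivers, but does not establish it.

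Finally, the stated purpose concerns the content of caregiver networks, and the valence and topic measures are set at the global network level. Circulating support messages could count as changed content. However, Hypothesis 1 is tested as within-subject change, and the circulation of study Tweets is already covered by the retweet count.

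**Conclusion.** The concern holds for the Hypothesis 1 pre-post change in valence and for topic change. As written, study-authored text can enter both outcomes in the later window and cannot enter at baseline, so a positive result could not be attributed cleanly to what caregivers write. Hypothesis 2 is exposed only if the share or tone of copied text differs between the communities.

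The magnitude is not known. Under assumed copied shares of 10% to 20% and gaps of 0.5 to 1 SD of follower-level change, the chance of a significant valence change with no change in caregivers' own writing runs from 14% to 93% at n = 300. These figures show that modest copying could matter; they do not predict the bias. The conclusion that the outcomes are open to this artefact rests on the scoring rule and the timing, and needs none of the assumed values.

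**What to change.** State in the analysis plan that the primary valence and topic analyses exclude study-authored text:

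- posts by the study accounts and chat hosts (partly a safeguard, since the Procedure text already names followers as the source);
- pure retweets of those posts;
- the quoted study text within quote Tweets and replies, keeping and scoring the words the follower added.

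Apply the rule with the user ID and type fields already collected. Report retweets of study Tweets as engagement only.

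Run two sensitivity analyses: one on all text, and one on follower-authored text only, with every pure retweet dropped in both windows. Dropping all retweets should not be the primary rule. It removes far more than study text and would cost the paired test followers for reasons unrelated to this defect.

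The cost is small: no new data and no change in sample size. Slightly fewer Tweets are scored, and followers who only retweet study posts have no later-window valence value. That loss may be related to engagement, so the number of such followers should be reported by community.
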